6.2 Screening Period/Pre-Study Evaluation

All patients must sign a written informed consent form before study specific screening procedures are performed. Screening procedures to evaluate patient eligibility will be conducted as per the schedule outlined below. If the patient meets eligibility and screening requirements he will return to the site for the day 1 visit and drug dispensation.

6.2.1 Establish baseline PSA doubling time and serum testosterone levelfor eligibility determination (within 3 months prior to day 1 of protocol therapy)

- Estimation of baseline PSA doubling time
 - Calculated based upon all serum PSA measurements obtained within 3 months prior to day 1 of protocol therapy, with a minimum of three PSA measurements each spaced at least 14 days apart.
 - PSA values obtained when serum testosterone was known to be less than 150 ng/dL, prior to local therapy, or within three months of last dose of LHRH agonist/antagonist or antiandrogen will be excluded from the calculation of the PSA doubling time.
 - Measurement of all PSA values included in determination of PSA doubling time recommended to be performed in the same laboratory
 - Actual calculation of the PSA doubling time can be obtained from the following online calculator: http://nomograms.mskcc.org/Prostate/PsaDoublingTime.aspx
 - Patients eligible if PSA doubling time is less than or equal to 15 months.
- Serum testosterone level
 - If no prior androgen deprivation therapy:
 - A single measurement greater than 150 ng/dL within 3 months of day 1 of protocol therapy
 - If prior androgen deprivation therapy (either in adjuvant or biochemical relapse setting):

The two most recent measurements of serum testosterone prior to study entry must fulfill the following criteria:

- Both measurements greater than 150 ng/dL,
- The two measurements are spaced at least 14 days apart
- Both must be measured within 3 months of day 1 of protocol therapy
- There must not be an increase of > 50 ng/dL between these two successive measurements

6.2.2 Clinical (within 28 days of day 1 of protocol therapy)

- Complete history and physical examination
- Baseline demographics

- Height and weight
- ECOG Performance Status
- Adverse Event Assessment

6.2.3 Laboratory (within 28 days of day 1 of protocol therapy)

- Complete blood count including differential and platelet count
- Total bilirubin, alkaline phosphatase, AST, ALT, BUN, creatinine, sodium, potassium
- Serum testosterone, androstenedione, DHEA-S, cortisol, aldosterone, deoxycortiocosterone, 11-deoxycortisol, and ACTH levels
- Plasma/serum and PBMCs for banking (Optional)

6.2.4 Radiographic Studies and Procedures (within 6 weeks of day 1 of protocol therapy)

The following will only be conducted if the patient is otherwise eligible for the study as per the laboratory/clinical parameters outlined above and has given written, informed consent.

- Radionuclide bone scan(either technetium-99 or Na-F radiolabel)
- Cross-sectional imaging of the abdomen and pelvis (CT or MRI). Use of IV contrast per individual investigator discretion.
- Skin biopsy (if additional consent is obtained).

6.3 Study Treatment

Patients will commence protocol therapy on Day 1 of study treatment. Patients will continue protocol therapy and remain on study until PSA progression (see Section 2 for definition), development of metastases, initiation of non-protocol therapy, unacceptable toxicity, or patient/physician withdrawal from the study, whichever occurs soonest. The study timeline is defined as Day 1 = first day of study treatment initiation. Subsequent study time points will be defined based on study calendar, irrespective of subsequent dose delays/interruptions (see Section 8 for discussion of dose delays due to toxicity).

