3.0 Study Design

3.1 Overall Study Characteristics

This is a phase II, single arm study of itraconazole dosed at 300 mg PO BID in patients with noncastrate, non-metastatic, biochemically relapsed prostate cancer after prior definitive local therapy. Simon''s two stage minimax design will be followed for accrual and include an interim test for lack of efficacy (see Sections 10.2 and 10.4). There is a pre-specified stopping rule for safety after 10 patients have been treated for a minimum of 8 weeks of protocol therapy (see Section 10.4). Patients will remain on protocol therapy until the first occurrence of any of the following: PSA progression, as defined in Section 2, development of metastasis, unacceptable toxicity, initiation of non-protocol therapy, or patient/physician withdrawal from study. Patients will remain on study until development of metastasis, initiation of non-protocol therapy, or patient/physician withdrawal from study, whichever occurs soonest. The total study duration including follow up is expected to be 3 years from the date of first patient enrolled onto study.

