6.1 Study Schedule

	Pre-Study	Cyc	cle 1	Cycle 2	Cycle 3	Cycle 4	Cycle 5 and beyond	End of Study
Procedure	Screening	Day 1	Day 8 (+/- 3 days)	Day 1 (+/- 7 days)	PSA or Clinical Progression			
Informed Consent ^a	Х							
Within 3 months of Cycle Day	y 1		1	1	1		1	
PSA ^b	X °	Х		Х	Х	Х	Х	Х
Serum Testosterone ^d	X ^e			Х		Х		Х
Within 6 weeks of Cycle Day	1						•	
Whole body bone scan + CT or MRI of and/pelvis ^f	Х							X ^g
Skin biopsy (optional) ^h	Х			Х				
Within 28 days (4 weeks) of C	ycle Day 1							
Demographics	Х							
History / Physical	Х	Х	Х	Х	Х	Х	Х	
Height/Weight	Х	Х	Х	Х	Х	Х	Х	
ECOG Performance Status	Х	X	X	Х	Х	Х	Х	
Toxicity Assessment	Х	Х	Х	Х	Х	Х	Х	Х
CBC w/diff and platelets	Х						Х	
BUN / Creatinine	Х						Х	
ALT, AST, AlkP, total bilirubin	Х		X	Х	Х	Х	Х	
Other serum hormones ^d	Х			Х		Х		Х

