6.4 Reasons for Treatment Discontinuation

Patients will discontinue protocol therapy and betreated per individual investigator discretion at the first occurrence of any of the following:

- PSA progression
- Development of overt metastases
- Patient or treating physician decision
- Unacceptable toxicity
- Non-protocol therapy

Patients who discontinue therapy due to development of metastases detected on radiographic tests, initiation of non-protocol therapy, or patient/physician decision will be removed from study at the time of protocol therapy discontinuation.

Patients who discontinue protocol therapy due to PSA progression or unacceptable toxicity will remain on study in follow up phase (see next section) until clinical progression.

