6.5 Follow Up

Patients will have a safety follow up visit 30 days after the last dose of study drug.

If patients discontinue protocol therapy due to PSA progression or unacceptable toxicity, they will be followed until the time of initiation of non-protocol therapy, development of metastases, or patient/physician withdrawal from study, whichever occurs soonest, at which point they will be taken off study.

During the follow up phase, the frequency of clinical/laboratory/radiographic assessment will beper individual investigator discretion.

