10.0 Planned Statistical Methods

10.1 Study Design

This is a phase II, single arm study of itraconazole dosed at 300 mg BID in patients with noncastrate, non-metastatic, biochemically relapsed prostate cancer after prior definitive local therapy. Simon's two stage minimax design will be followed for accrual and include an interim test for lack of efficacy (see Sections 10.2 and 10.4). There is a pre-specified stopping rule for

safety after 10 patients have been treated for a minimum of 8 weeks of protocol therapy (see Section 10.4). Patients will remain on protocol therapy until the first occurrence of any of the following: PSA progression, as defined in Section 2, development of metastasis, unacceptable toxicity, initiation of non-protocol therapy, or patient/physician withdrawal from study. Patients will remain on study until development of metastasis, initiation of non-protocol therapy, or patient/physician withdrawal from study, whichever occurs soonest. The total study duration including follow up is expected to be 3 years from the date of first patient enrolled onto study.

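### Section 6.3 ends study participation at PSA progression or toxicity, while Sections 3.1, 6.4, 6.5 and 10.1 follow those men to clinical progression; where 6.3 is applied, clinical-progression and metastasis events are lost

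*Combined protocol and SAP*

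**What the plan says.** Section 6.3 uses one list of events for two purposes: "Patients will continue protocol therapy and remain on study until PSA progression (see Section 2 for definition", or metastases, non-protocol therapy, unacceptable toxicity or withdrawal, whichever is first. The last column of the schedule in 6.1 is labelled End of Study and timed at "PSA or Clinical Progression". No column follows it.

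Section 3.1 separates the two. PSA progression and toxicity end therapy, but for participation: "Patients will remain on study until development of metastasis, initiation of non-protocol therapy, or patient/physician withdrawal from study, whichever occurs soonest". Section 10.1 repeats this. Section 6.4 says that men who stop "due to PSA progression or unacceptable toxicity will remain on study in follow up phase (see next section) until clinical progression". Section 6.5 agrees: "If patients discontinue protocol therapy due to PSA progression or unacceptable toxicity, they will be followed until the time of initiation of non-protocol therapy", metastases or withdrawal. It sets no visit schedule: "During the follow up phase, the frequency of clinical/laboratory/radiographic assessment will beper individual investigator discretion".

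Three other statements bear on the point. The abstract has follow-up lasting through survival. Section 6.4 says: "Patients who discontinue therapy due to development of metastases detected on radiographic tests, initiation of non-protocol therapy, or patient/physician decision will be removed from study", whereas 3.1 speaks of withdrawal from the study. Section 10.8.2 excludes PSA-only progression from clinical progression and does not list PSA progression as a reason for censoring. It does censor men who stop for toxicity at their last recorded study visit.

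**The concern.** Time to clinical progression and metastasis-free survival (analysed in 10.8.2 as time to first metastasis) are stated secondary objectives. Both need observation beyond PSA progression: clinical progression excludes it by definition, and non-protocol therapy will often be started because of it. A man taken off study under 6.3 has his last study visit at PSA progression and would presumably be censored there.

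That censoring is probably informative. For clinical progression, the chance of starting other therapy is likely to rise just after a man leaves the risk set, so the Kaplan-Meier median would be too long. For metastasis, Section 1.3.3 itself reports an association between PSA kinetics and metastasis-free survival: landmark medians of 63.5 and 28.9 months for men with and without a decrease in PSA slope. If the three sites applied different sections, their men would be censored by different rules.

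**Working it through.** **1. Who is still on study, by section**

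| Place | After PSA progression | After unacceptable toxicity | After a decision only to stop drug |
|---|---|---|---|
| 6.3 | off study | off study | names withdrawal from the study only |
| 3.1, 10.1 | on study | on study | name withdrawal from the study only |
| 6.4 | on study to clinical progression | on study to clinical progression | removed from study |
| 6.5 | followed | followed | 30-day safety visit only |
| Abstract | followed through survival | followed through survival | followed through survival |

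The first two columns cannot all be obeyed.

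**2. The plan's own figures.** The documents give no event count, power or expected median for clinical progression or metastasis. The stated figures concern the primary endpoint (10.2): 22 then 40 patients, continue if more than 2 responses, reject the null with at least 8, response rates 10% against 25%. The exact two-stage binomial calculation gives an early stopping probability of 0.620 (stated 0.62), type I error 0.0398 (limit 0.05) and power 0.803 (stated 0.80). None of these depends on follow-up after PSA progression.

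**3. How early PSA progression could come.** The rule needs a rise above 50% and above 2 ng/mL. With an inactive drug, constant doubling time (PSADT) and baseline PSA b, the threshold is reached at log2(max(1.5, (b+2)/b)) × PSADT.
- b of 4 ng/mL or more: log2(1.5) = 0.585, so 1.8, 3.5, 5.8 and 8.8 months at PSADT 3, 6, 10 and 15 months.
- b = 1 ng/mL (entry minimum after prostatectomy): log2(3) = 1.585, so 4.8 to 23.8 months at PSADT 3 to 15 months.

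**4. Follow-up available.** Accrual takes about 14 months and the study 3 years (10.3), so each man has 36 − 14 = 22 to 36 months, mean 29.

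**5. Events lost if all men are closed as in 6.3.** This is an illustration on assumptions that are not in the documents: exponential times; median to PSA progression 6, 12 or 18 months; median to metastasis 30 or 60 months, independent of PSA progression; non-protocol therapy starting a median 3, 6 or 12 months after PSA progression and never before it; uniform accrual over 14 months; data cut at 36 months. As in 10.8.2, non-protocol therapy censors metastasis. Selected results per 40 men (medians in months for PSA progression / metastasis / delay to non-protocol therapy):

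| Medians | Clinical progression: followed → closed (lost) | Metastasis: followed → closed (lost) |
|---|---|---|
| 6 / 60 / 3 | 37.8 → 3.5 (91%) | 5.1 → 3.5 (31%) |
| 6 / 60 / 12 | 30.0 → 3.5 (88%) | 7.9 → 3.5 (56%) |
| 12 / 30 / 6 | 32.8 → 10.3 (69%) | 14.0 → 10.3 (27%) |
| 18 / 30 / 3 | 31.7 → 12.4 (61%) | 14.2 → 12.4 (12%) |
| 18 / 30 / 12 | 27.4 → 12.4 (55%) | 16.7 → 12.4 (26%) |

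Over all 18 combinations the loss is 55-91% for clinical progression and 12-56% for metastasis.

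Hand check of the first row: the chance that metastasis precedes PSA progression is 6/(6+60) = 0.091. The combined hazard is 0.693 × (1/6 + 1/60) = 0.127 per month, so by 29 months 1 − exp(−0.127 × 29) = 0.975 of first events have occurred. Then 40 × 0.091 × 0.975 ≈ 3.5.

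Two limits apply. The high loss for clinical progression follows largely from assuming that non-protocol therapy never precedes PSA progression; under 6.3 only metastases then remain as events. And metastases already visible on the scan required at PSA progression (6.3.5) are not credited separately, which would lower the losses.

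**The case against.** The strongest reply is that the plan already directs the right conduct. Four sections keep these men on study, two of them the specific discontinuation and follow-up sections, and 10.8.2 fits them because PSA progression is not a censoring reason. Against that stands one clause in a treatment section. This is fair: it shows which rule was intended, and it makes the loss conditional on a site applying 6.3. It does not remove the contradiction.

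The schedule column is weak support for 6.3. Its timing also covers clinical progression, its contents match the assessments that 6.3.5 and 9.1 require at that event, and 6.5 leaves later frequency to the investigator, so no fixed follow-up column is expected.

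A reader might infer from step 3 and the medians in 1.3.3 that almost all metastases would fall after study exit. The documents do not support that. The short times apply at baseline PSA of 4 ng/mL or more; near 1 ng/mL they reach 23.8 months. The 28.9 and 63.5 months are landmark medians for two subgroups, not a general range. With 22 to 36 months of follow-up, many metastases would be missed under any reading. The scan at PSA progression keeps those visible then. Nor do the documents show that data from different sites could not be pooled; they would be censored differently.

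On 6.4, Section 3.1 lists withdrawal from the study as a reason therapy ends, so it may treat stopping by decision and leaving the study as one event. That is unclear wording rather than a proven conflict.

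**Conclusion.** The contradiction is certain from the text: 6.3 closes men at PSA progression or toxicity, 3.1, 6.4, 6.5 and 10.1 do not, and the abstract says something else again. Its effect is conditional. Where 6.3 is applied, both endpoints would be censored at PSA progression, probably informatively. On the assumptions in step 5 and with all sites applying 6.3, roughly half to nine-tenths of clinical-progression events would be lost, and a smaller share of metastasis events, 12-56% before crediting the scan. If only some sites apply it, the loss is smaller.

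It would be too strong to say that the objectives lose their events as the plan stands, since most of the text directs the follow-up they need. The analyses are described as exploratory in 5.3.2.2, and the primary endpoint and sample size do not change. The wording should be corrected because the remedy is cheap and the affected estimates are meant to inform later trials.

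A related conflict needs settling too. Section 10.8.2 censors toxicity discontinuations at the last recorded study visit, while 6.4 and 6.5 keep those men in follow-up, so it is unclear whether their later events count.

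**What to change.** - **6.3:** remove the words that tie study participation to the listed events, so that they end protocol therapy only, and refer to 3.1, 6.5 and 10.1 for study exit. The list of events that end therapy is untouched.
- **6.1:** relabel the End of Study column as the PSA or clinical progression visit. Add a line to record the dates of first metastasis and first non-protocol therapy during the follow-up planned in 6.5.
- **Abstract:** reconcile the follow-up statement with these sections.
- **10.8.2:** reconcile the censoring of toxicity discontinuations with 6.4 and 6.5, so that events seen in their follow-up count.
- **6.4 and 3.1:** reconcile stopping by patient or physician decision with withdrawal from the study.

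The cost is a wording amendment and two dates on a case report form. For men who stop for PSA progression or toxicity, no visit or test is added, since 6.5 already plans their follow-up. If men who only stop drug by decision are also to be followed, that is a small addition, because beyond the 30-day safety visit 6.5 does not now cover them.

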6.3.1 Day 1 of Study Treatment

Patients will return to study site for a history and physical exam including weight, adverse event and con meds assessment, ECOG, measurement of serum PSA, and dispensing of study drug. The starting dose of itraconazole will be 300 mg PO BID, taken as 3 (100 mg) capsules twice daily with meals.

6.3.2 Dose Modifications

Both dose interruptions and dose reductions will be permitted for toxicity, as outlined in Section 8.

6.3.3 Concomitant Medications

Concomitant medications will be recorded at each monthly clinic visit. No concomitant use of any anti-neoplastic therapy will be permitted.

This will include:

- Surgery
- Radiation therapy
- Other secondary hormonal therapies including antiandrogens, 5-alpha reductase inhibitors (i.e. Finasteride, dutasteride), megestrol acetate
- Immunotherapy
- Chemotherapy
- Or other investigational agents

Nutritional supplements containing saw palmetto, pomegranate extract, or pomegranate juiceare also specifically prohibited. See Appendix 1 for a full list of medications and substances that are prohibited while taking itraconazole.

Patients may not currently be taking drugs that significantly interact with CYP3A4. A list of medications and substances with the potential to interact with itraconazoleare provided in Appendix 2. Patients taking digoxin should have serum digoxin levels monitored frequently; patients on warfarin should have INR levels measured regularly.

Because of the potential for drug-drug interaction, the electronic case report form (eCRF) must capture the concurrent use of all other drugs, over-the-counter medications, or alternative therapies.

6.3.4 Safety Assessment

Patients will be assessed for adverse events at Day 1 (for baseline) and Day 8, week 4, and every 4 weeks thereafterwhile receiving protocol therapy. Adverse events will be graded according to CTCAE version 4.03 (available at http://ctep.cancer.gov). Adverse events will be assessed by the individual investigator as definitely, probably, possibly, unlikely, or not related to study drug. Laboratory measurement is outlined below in Section 6.3.5. Additional laboratory measurements are at the discretion of the treating physician.

6.3.5 Laboratory/Radiographic Assessment

The frequency and schedule of laboratory and radiographic assessment is outlined above in the study schedule. Serum PSA will be measured on a monthly basis while patients are receiving protocol therapy. A whole body bone scan (either Na-F PET or technetium-99 bone scan), along with cross-sectional imaging of the abdomen/pelvis (CT or MRI) will be obtained at baseline and at the time of PSA or clinical progression, whichever occurs first.

Liver function tests and serum sodium and potassium levels will be measured pre-study, on day 8 +/- 3 days, day 28 +/- 7 days, then every 4 weeks +/- 7 days thereafter. BUN/serum creatinine will be measured pre-study and every 4 weeks +/- 7 days.

Serum itraconazole and hydroxy-itraconazole levels will be measured at the day 28 (+/- 7 days) study visit. Hormone levels (outlined above in the study schedule) will be measured at baseline, day 28 (+/- 7 days), and week 12 (+/- 7 days) of protocol therapy.

6.3.6 Skin Biopsy

For patients who sign additional consent form, a 3 mm punch biopsy of non-scalp skin containing hair follicles (will be obtained at baseline (within 6 weeks of Day 1 of protocol therapy) and day 28 ± 7 days of protocol therapy. Serial skin biopsies are an optional part of this study.

6.4 Reasons for Treatment Discontinuation

Patients will discontinue protocol therapy and betreated per individual investigator discretion at the first occurrence of any of the following:

- PSA progression
- Development of overt metastases
- Patient or treating physician decision
- Unacceptable toxicity
- Non-protocol therapy

Patients who discontinue therapy due to development of metastases detected on radiographic tests, initiation of non-protocol therapy, or patient/physician decision will be removed from study at the time of protocol therapy discontinuation.

Patients who discontinue protocol therapy due to PSA progression or unacceptable toxicity will remain on study in follow up phase (see next section) until clinical progression.

6.5 Follow Up

Patients will have a safety follow up visit 30 days after the last dose of study drug.

If patients discontinue protocol therapy due to PSA progression or unacceptable toxicity, they will be followed until the time of initiation of non-protocol therapy, development of metastases, or patient/physician withdrawal from study, whichever occurs soonest, at which point they will be taken off study.

During the follow up phase, the frequency of clinical/laboratory/radiographic assessment will beper individual investigator discretion.

6.6 Duration of Study

The total duration of the study including follow up is expected to be approximately 3 years from the date the first patient is enrolled onto study.

7.0 Study Drug Information

7.1 Itraconazole

Drug Substance: Itraconazole is an almost white to slightly yellow powder.

Chemical Name:(±)-cis-4-[4-[4-[4-[2-(2,4-dichlorophenyl)-2-(1H-1,2,4-triazol-1-ylmethyl)-1,3-dioxolan-4-yl]methoxy]phenyl]-1-piperazinyl]phenyl]-2,4-dihydro-2-(1-methylpropyl)-3H-1,2,4-triazol-3-one

Molecular Formula: C35H38Cl2N8O4

Molecular Weight: 705.64

Formulation: Itraconazole is available as pink and blue capsules containing 100 mg of itraconazole in a pellet formulation. Each capsule contains 100 mg of itraconazole as well as: sugar spheres (NF), hydroxypropylmethylcellulose, gelatin, polyethylene glycol, titanium dioxide, FD&C Blue No. 1, FD&C Blue No. 2, D&C Red No. 22 and D&C Red No. 28. The pKa of itraconazole is 3.7 with a melting range of 165-169 degrees Celsius.It is highly hydrophobic and lipophilic, with a log partition coefficient of 5.66 in the n-octanol/aqueous buffer solution of pH=8.1. Itraconazole is very poorly soluble in water (<1 μ g/mL) and in diluted acidic solutions (<5 μ g/mL).

Route of Administration:Itraconazole 100 mg capsules are administered orally. Absorption of itraconazole is impaired when the gastric pH is increased. Capsules should be taken after a meal. If a patient is taking a concurrent proton pump inhibitor or H2-antagonist, it is advisable that itraconazole be taken in conjunction with an acidic beverage such as a cola product or orange juice to increase absorption. Grapefruit juice is not recommended due the potential drug interaction with itraconazole.

Pharmacokinetics:

Absorption: Better absorbed with food and lower gastric pH.

Distribution: V_d (average): 796 ± 185 L or 10 L/kg; highly lipophilic and tissue concentrations are higher than plasma concentrations. The highest concentrations: adipose, omentum, endometrium, cervical and vaginal mucus, and skin/nails. Aqueous fluids (eg, CSF and urine) contain negligible amounts.

Protein binding, plasma: 99.8%; metabolite hydroxy-itraconazole: 99.5%

Metabolism: Extensively hepatic via CYP3A4 into >30 metabolites including hydroxyitraconazole (major metabolite); appears to have *in vitro* antifungal activity. Main metabolic pathway is oxidation; may undergo saturation metabolism with multiple dosing.

Bioavailability: Variable, ~30-40%% (capsule). *Half-life elimination:* Oral: Single dose: ~21 hours, steady state: 64 hours; Cirrhosis (single dose): 37 hours (range 20-54 hours) *Time to peak, plasma:* 3-5 hours *Excretion:* Urine (<0.03% active drug, 40% as inactive metabolites); feces (~3% to 18%)

Storage and Handling: Itraconazole capsules are supplied in HDPE bottles of 30. They should

be stored at room temperature (15-30 degrees Celsius) and protected from light and moisture.

Dose: 300 mg PO BID. Three 100 mg capsules taken twice daily with food (6 capsules per day in total).

Possible Anticipated Adverse Events: The most frequently reported adverse events in prior clinical trials of itraconazole were gastrointestinal in nature, including diarrhea, nausea and/or vomiting, anorexia, or abdominal pain. Other potential adverse events include peripheral edema, hypertension, hypokalemia, fatigue, and elevated liver enzymes. Rare but serious and potentially life threatening adverse events include adrenal insufficiency, allergic reactions including Stevens-Johnson syndrome, congestive heart failure, and liver failure. Itraconazole may also potentially interact with a number of other medications and herbal supplements, so a careful review of the concurrent medications is warranted during therapy (see Appendix 2 for list of potential interacting medications to avoid while on itraconazole therapy).

Dispensing of Drug: A 28 day supply of study drug will be provided to patients at each study visit every 4 weeks.

Inventory and Control: The itraconazoleused for this study must be maintained under adequate security and stored in the pharmacy at the study site until dispensing or their return to the UCSF Helen Diller Family Comprehensive Cancer Center investigational pharmacy. Investigators may not supply study medication to any person not enrolled in this study or to any person not named as a sub-investigator.

In addition, the investigator must maintain an accurate, running inventory of all drug supplies received and dispensed during conduct of the study. At the completion of the study, a copy of the final inventory will be supplied to the UCSF Helen Diller Family Comprehensive Cancer Center investigational pharmacy. The original will be retained by the investigator in the study files.

Return of Clinical Supplies: Upon completion or termination of the study, all used and unused original study drug bottles, whether empty or containing study drug, will be returned to the UCSF Helen Diller Family Comprehensive Cancer Center investigational pharmacy. Return shipments must provide proof of delivery, and will be accompanied by the Drug Accountability Form and a memo noting the number of bottles and quantity of study drug being returned.

